Patients will be followed on a daily basis for 28 days or until they leave the intensive care unit or die. If a patient is transferred to a progressive care or step-down unit and continues to receive ventilation, the patient will be followed on a daily basis until the patient is extubated or dies or until day 28. If a patient is extubated and reintubated before day 28, the patient will continue to receive ventilation according to the group to which the patient was originally randomized.

IRB Protocol: _____

Site PI: _____

Version Date: 2/9/2020

Page 10 of 34

Intervention to be tested

The intervention we will test is adding sigh breaths, consisting of an increase in PEEP that produces a plateau pressure (Pplat) of 35 cmH₂O (or 40 cmH₂O in patients with BMIs > 35, in patients with moderate or severe abdominal distension from ascites, blood and/or ileus, or prone patients). The sigh breaths will be delivered once every 6 minutes, as part of usual invasive mechanical ventilation.

The rate of delivery of these sigh breaths was selected on the basis of several studies. Bendixen and colleagues (1964) documented that the rate at which sighs occurred in normal humans was approximately 10/hour. Mead and Collier (7) showed that sighs given only six times/hour prevented the reduction in compliance that occurred with constant V_T ventilation in animals with normal lungs and Reiss and colleagues (2011) found that a single sigh given once every 5 min improved mechanics, gas exchange and inflammatory cytokines in normal mice. Frick and colleagues (2004) reported that lamellar body fusion preceding surfactant secretion that was increased by applying a single stretch of isolated type II cells abated by 5 min and Steimback and colleagues (2009) found that delivering one sigh every 6 min reduced epithelial cell apoptosis and procollagen III expression and improved respiratory mechanics in rats with experimental lung injury compared with animals not receiving sighs and those receiving three sighs/min.

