The plateau change resulting from increasing PEEP producing a Pplat of 35 or 40 cmH₂O was selected for two reasons. First, it produces an end-inspiratory lung volume that approximates total lung capacity in patients with normal chest wall and lung compliances, thereby facilitating secretion of surfactant. Second, a Pplat of 40 cmH₂O has been utilized in numerous short-term studies of recruitment maneuvers in patients with ARDS without any evidence that it caused barotrauma or volutrauma (Pelosi, 1999; Oczenski, 2005; Grasso, 2002; Lim, 2003; Antonaglia, 2006). In patients with clinically evident abdominal distension graded moderate or severe, in those with BMI's exceeding 35, and in those who are prone the volume of the sigh breath will be determined on the basis of a Pplat of 40 cmH₂O given the decrease in chest wall compliance that will be present in these situations. Patients who have reached maximum PEEP and cannot obtain goal Pplat will not be considered deviations and the reasons for not reaching goal will be recorded by study personnel.

At present there is only one mechanical ventilator available in the U.S. that is configured to provide sigh breaths as designed, the Drager Evita Infinity V500.

For patients receiving invasive mechanical ventilation prior to admission to the ICU, the intervention will begin as soon as possible, but not longer than 24 hours after the patient was placed on mechanical ventilation. For patients who are intubated and placed on invasive mechanical ventilation at some time after admission to the ICU, the

IRB Protocol: _____

Site PI: _____

Version Date: 2/9/2020

Page 11 of 34

intervention will begin as soon as possible, but within 24 hours of starting invasive mechanical ventilation.

If a patient is randomized to receive sigh breaths and is transported to the operating room, CT, IR or other hospital department after randomization, the patient should be ventilated according to usual practice, i.e., they need not continue to receive sigh breaths during the time they are away from the ICU. Sigh breaths should be restarted on their return.

Endpoints

1. The primary endpoint in this study is the number of ventilator-free days (VFDs) to day 28 after enrollment. VFDs will be counted in the following fashion:

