 - iii. If no, is the P_{plat} for the sigh breath $35 \text{ cmH}_2\text{O}$?

IRB Protocol: _____

Site PI: _____

Version Date: 2/9/2020

Page 15 of 34

- e. Level of PEEP applied during sighs to produce a Pplat of 35 or 40 cmH₂O
- f. Transfusions of any blood products (in units, includes red blood cells, fresh frozen plasma, platelets and/or whole blood)
- g. Does the patient have an abdominal distention (yes/no)? If yes, is it mild, moderate or severe?
- h. Whether the patient is receiving any of the following medications (yes/no)
 - i. Vasopressors (includes norepinephrine, vasopressin, epinephrine, phenylephrine, isoproterenol and dopamine). Indicate all that were administered
 - ii. Inotropic agents (includes dobutamine, milrinone, amrinone).
 - iii. Paralytics If yes, indicate reason (ventilator dyssynchrony, other)
 - iv. Benzodiazapine (diazepam, lorazepam, midazolam)
 - v. Dexmetatomidine
 - vi. Propofol
 - vii. Other (haloperidol, phenobarbital, droperidol, quetiapine)
- i. Most recent Richmond Agitation-Sedation Scale (RASS) score before randomization
- j. Does the patient have a tube thoracostomy?
 - i. If yes, what was the timing (on admission, after admission but within the first 24 hours or before the initial assessment)?
 - ii. Reason for the tube thoracostomy (pneumothorax, hemothorax, both)
- k. Did the patient undergo an operation after admission but within the first 24 hours or before the initial assessment? If yes, provide date/time for each operation and a description of the operation.
- l. Were any infiltrates identified? If yes, indicate which area or areas:
 - i. Left upper (including left middle area)
 - ii. Left lower
 - iii. Right upper (including right middle area)
 - iv. Right lower

3. Daily Assessments

- a. Use of continuous invasive mechanical ventilation
- b. Ventilator used, ventilator mode, tidal volume, F_iO₂, PEEP, peak and plateau pressures, prone positioning
- c. The latest arterial blood gas prior to the ventilator settings recorded, indicating pH, the PaCO₂, the PaO₂, the HCO₃, the FIO₂, the SaO₂ and the PEEP level and the time the sample was obtained
- d. Were any infiltrates identified? If yes, indicate area:

IRB Protocol: _____

Site PI: _____

Version Date: 2/9/2020

Page 16 of 34

- i. Left upper (including left middle area)
- ii. Left lower
- iii. Right upper (including right middle area)
- iv. Right lower

e. Are the infiltrates:

- i. Unchanged from previous film

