- ii. Worse or more extensive than on previous film
- iii. Better than on previous film

f. Ejection Fraction (EF) if echocardiogram was obtained.

g. Whether the patient is receiving any of the following medications (yes/no)

- i. Vasopressors (includes norepinephrine, vasopressin, epinephrine, phenylephrine, isoproterenol and dopamine). Indicate all that were administered
- ii. Inotropic agents (includes dobutamine, milrinone, amrinone).
- iii. Paralytics If yes, indicate reason (ventilator dysynchrony, other)
- iv. Benzodiazepine (diazepam, lorazepam, midazolam)
- v. Dexmetatomidine
- vi. Propofol
- vii. Other (haloperidol, phenobarbital, droperidol, quetiapine)

h. Most recent Richmond Agitation-Sedation Scale (RASS) score

i. Use of prone positioning or inhaled NO > 12 hr in last 24 hrs (y/n)

j. Date and time of discontinuation of invasive mechanical ventilation

k. Did patient receive non-invasive mechanical ventilation (CPAP > 5 cmH₂O, BiPAP other than for OSA)

l. Date and time of reinstitution of invasive mechanical ventilation (if necessary)

m. Date and time of transfer out of ICU to day 28 (if occurred)

n. Date of hospital discharge to day 28 (if occurred)

o. Date and cause of death to day 28 (if occurred)

p. Assessment of abdominal distension (mild, moderate, severe)

q. Did the patient undergo an operation in the previous 24 hours (laparotomy, thoracotomy, craniotomy, rib plating, ORIF, other)

r. Presence of pneumothorax or pneumatocele

s. Tracheostomy in the past 24 hours?

t. BAL or mini-BAL with colony counts if available

u. Is alcohol withdraw affecting management

v. Occurrence of complications (e.g., cardiac arrest, stroke, MI, PE, AKI, pneumonia, ICP related to the vent mode)

IRB Protocol: _____

Site PI: _____

Version Date: 2/9/2020

Page 17 of 34

4. Closeout assessments

- a. Final 28-day disposition (e.g., discharged or transferred to home or elsewhere if alive)
- b. Discharge diagnoses (ICD9 or ICD10 codes)
- c. Procedures (CPT codes)
- d. Chest AIS
- e. Description of trauma
- f. ISS
- g. Mechanism of injury
- h. Rib plates
- i. Discharged on new continuous home oxygen

Statistical plan

Sample size estimate

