In the first of these, Pelosi and colleagues (1999) delivered three consecutive sigh breaths/min to a Pplat of 45 cmH₂O for one hour to 10 patients with ARDS. Prior to instituting the sighs the patients were receiving a mean VT of 0.56 ± 0.11 L and a PEEP of 14 cmH₂O. Accordingly, the patients had more severe lung injury than those we are planning to study. During the period when sigh breaths were delivered the VT's increased to 1.1 ± 0.45 L. Pulmonary arterial pressure decreased 2.5 ± 1.9 mmHg and pulmonary vascular resistance decreased 30.8 ± 27.8 dyne•sec•cm⁻⁵•m⁻² and both returned to control values after the sighs were discontinued. No instances of barotrauma were reported. These small but significant hemodynamic changes are not likely to be encountered in the study we propose as they were seen when three sighs were administered each minute whereas we are proposing to deliver one sigh every 6 minutes.

In the second, Foti and colleagues (2000) raised PEEP from 9.4 ± 3 to 16 ± 2 cmH₂O for two breaths separated by 30 sec, twice a minute for 30 minutes in 15 patients with ARDS. Peak inspiratory pressure averaged 35.5 ± 5.4 cmH₂O during the period in which sighs were instituted. Cardiac out, mean arterial blood pressure, pulmonary arterial pressure, pulmonary arterial wedge pressure, central venous pressures and oxygen delivery did not change. No instances of barotrauma were reported.

Patroniti and colleagues (2002) utilized one sigh breath/min, each lasting 3 to 5 seconds by intermittently raising PEEP to produce a Pplat that was 20% higher than the Pplat under the control condition or 35 cmH₂O, whichever was higher, for one hour in 13 patients with ARDS. Pplat averaged 38 ± 3.2 cmH₂O during the period when sighs were applied corresponding to VT's of 1.15 ± 0.3 L that were delivered on top of PEEP levels that averaged 10 ± 4 cmH₂O. Heart rate, systolic and diastolic blood pressure did not change. No instances of barotrauma were reported. This study indicates that limiting our Pplat to 40 cmH₂O (45 cmH₂O in those with a BMI > 30) will allow us to achieve increases in VTs that are sufficient to cause surfactant release.

IRB Protocol: _____

Site PI: _____

Version Date: 2/9/2020

Page 24 of 34

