In a second study, Pelosi and colleagues (2003) delivered three consecutive sigh breaths/min to a P_{plat} of 45 cmH₂O (that corresponded to a V_T of 947 ± 321 mL) for one hour to 10 patients with ARDS. Prior to administering sigh breaths the patients were being ventilated with a V_T of 590 ± 138 mL and a PEEP of 14 ± 3 cmH₂O. No change in hemodynamics occurred and no instances of barotrauma were reported.

Accordingly, although the number of patients studied is small but the literature contains no suggestion that the sigh breaths in volumes that we propose to deliver will cause any hemodynamic compromise. In addition, using a P_{plat} of 35 or 40 cmH₂O is below that used by other investigators in patients who had more severe lung injury than those we will be studying and no instances of barotrauma were observed.

b. Ventilator-induced lung injury (VILI)

VILI is attributed to overdistension and/or to cyclical airspace opening and closing. Low V_T ventilation is now the standard of care for patients with ARDS and is thought to reduce VILI by reducing overdistension. The lung volume produced by a P_{plat} of 35 or 40 cmH₂O could result in overdistension in some areas of the lung in some patients. It seems unlikely, however, that VILI could occur from this degree of overdistension occurring only 10 times/hour, and studies in animal models of lung injury indicate that such a strategy is protective rather than injurious (Oyarzun, 1977; Mascheroni; 1988; Oyarzun, 1991; Pelosi, 1999; Patroniti, 2002). Nonetheless, VILI remains a potential adverse effect. Nonetheless, we will perform two interim analyses of the data looking for evidence that there might be *fewer* VFDs in the intervention arm of the study than in the control (i.e., a result opposite to the one hypothesized) and the stopping rules for harm are less stringent than those for documenting benefit (see above). In addition, respiratory therapists will, on at least a daily basis, confirm that the sigh breaths being delivered do not result in a P_{plat} that exceeds 40 cmH₂O (45 cmH₂O in patients with decreased chest wall compliance as described above). Adjustments in the volumes or P_{plat} will be made as needed. In addition these pressures will be rechecked whenever the treating physician is concerned about a change in the patient's clinical status. The frequency with which these adjustments are needed will be recorded.

c. Patient-ventilator dyssynchrony

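### The daily bedside check on sigh plateau pressure is set 5 cmH₂O above the prescribed dose in both tiers, and no tolerance above goal is stated

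*Combined protocol and SAP*

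**What the plan says.** **Dose.** Under Intervention to be tested, the sigh is a rise in PEEP that "produces a plateau pressure (Pplat) of 35 cmH₂O (or 40 cmH₂O in patients with BMIs > 35". The 40 tier also covers moderate or severe abdominal distension and prone position. The section explains this tier by the chest wall: the sigh "will be determined on the basis of a Pplat of 40 cmH₂O given the decrease in chest wall compliance". On safety it notes that "a Pplat of 40 cmH₂O has been utilized in numerous short-term studies of recruitment maneuvers in patients with ARDS". It addresses departures from goal in one direction only: patients at maximum PEEP who "cannot obtain goal Pplat will not be considered deviations".

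**Forms.** Data collection, Initial assessment, uses the same pair. Items 2d(i)–(iii) ask whether the sigh plateau pressure is 40 if BMI exceeds 35, and 35 if it does not. Item 2e records "Level of PEEP applied during sighs to produce a Pplat of 35 or 40 cmH₂O".

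**Safety text.** In Risk/Benefits Assessment, the conclusion of part a (Baro- or volutrauma) and the overdistension discussion in part b (VILI) both refer to 35 or 40. Earlier in part a, however, the protocol speaks of "limiting our Pplat to 40 cmH₂O (45 cmH₂O in those with a BMI > 30".

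**Check.** Part b then says that respiratory therapists will confirm, at least daily, that sighs "do not result in a P_{plat} that exceeds 40 cmH₂O (45 cmH₂O in patients with decreased chest wall compliance as described above". Pressures are also rechecked when the treating physician is concerned about a change in clinical status, and adjustments are made where necessary.

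**The concern.** Part b offers two protections against lung injury from the sighs: interim analyses of ventilator-free days, and this check. Only the check operates at the bedside for the individual patient. A check on a prescribed pressure should be tied to that pressure, or to a stated margin above it. Here the limits belong to a different pair of numbers, and the nearby barotrauma clause attaches that pair to a different BMI cut-off.

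Two things are at stake. The first is fidelity to the dose: the check does not separate the two tiers. The second is the safety argument: in the high tier the check tolerates a pressure that the protocol's own comparison with earlier studies does not cover. The protocol concedes, under Foreseeable risks, that it found no human studies giving sighs in a similar way, so the stated bedside limit deserves care.

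**Working it through.** The plan states the limit without deriving it, so there is no figure to reproduce. The check is a side-by-side comparison.

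**Inputs**

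| Source | Default | High tier | Who is in the high tier |
|---|---|---|---|
| Intervention to be tested (dose) | 35 | 40 | BMI > 35, moderate or severe distension, prone |
| Initial assessment 2d(i)–(iii) | 35 | 40 | BMI > 35 only |
| Part a, conclusion; part b, overdistension | 35 | 40 | not restated |
| Part a, earlier clause | 40 | 45 | BMI > 30 |
| Part b, daily check | 40 | 45 | decreased chest wall compliance |

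All pressures are in cmH₂O. The dose section gives decreased chest wall compliance as the reason for the 40 tier. The group that the check allows to reach 45 is therefore best read as the group dosed at 40.

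**Gap = limit − dose**

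- Default: 40 − 35 = 5; 5/35 = 14.3% above dose.
- High tier: 45 − 40 = 5; 5/40 = 12.5% above dose.

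**What the check flags.** It flags a sigh only if plateau pressure exceeds the limit.

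- Default patient whose sigh reaches 40: 40 is not above 40, so it passes, 5 over dose.
- Patient dosed at 40 while prone or distended, now supine or no longer distended, whose sigh still reaches 40: the dose is again 35 and the limit 40, so it passes.
- High-tier patient whose sigh reaches 45: 45 is not above 45, so it passes, 5 over dose.

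With limits of 35 (40), each of these exceeds the limit by 5 and is flagged unless the stated tolerance is 5 or more.

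**Safety text at the limits.** A pressure of 40 is covered: the dose section cites recruitment studies at 40, and parts a and b discuss 35 or 40. A pressure of 45 is different. Part a concludes that 35 or 40 is lower than other investigators used. The highest sigh plateau pressure it describes is 45, in two ARDS studies of 10 patients each. At 40 the comparison holds against those two studies; at 45 the pressures are equal, so it does not.

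**Other controls.** Items 2d(i)–(iii) compare the sigh with dose, but they sit in the initial assessment and are keyed to BMI alone. The Daily Assessments include "Assessment of abdominal distension (mild, moderate, severe" (item 3p) and prone position (items 3b and 3i), so the information that sets the tier is collected. Item 3b asks for plateau pressure without saying whether it is the sigh's.

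**The case against.** The strongest reply is that a target and a ceiling can coexist. The dose section sets a goal of 35 (40), part b sets a bound of 40 (45), and the same 5 cmH₂O offset in both tiers could be a deliberate margin. A hard limit equal to the goal would flag ordinary measurement variation. This stands as a possibility, and the documents do not settle it. But no text calls the 5 cmH₂O a margin, and only failure to reach goal is excused. The earlier clause in part a presents 40 (45) as sufficient for the tidal volumes needed to release surfactant, which reads more like a dose than a tolerance. As a ceiling, 45 would still lie outside the part a comparison, and the BMI cut-off would still conflict.

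Some stronger readings are tempting but not supported:

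- *That patients are exposed to unassessed or harmful pressures.* The protocol does assess 40, and it reports no barotrauma in the two studies at 45, although those lasted one hour. The prescribed dose still applies, and nothing shows that patients receive more.
- *That the 45 limit alone undermines the comparison with earlier work.* The other two sigh studies described averaged a plateau pressure of 38 and a peak pressure of 35.5, so 40 is already above both. That weakness exists at the prescribed dose.
- *That nothing checks the dose.* Items 2d(i)–(iii) do so once, site visits review adherence, and the Manual of Procedures, which is not among the documents, may give therapists a tighter limit.
- *That the gap is 10 cmH₂O for BMI between 30 and 35 (45 − 35).* This requires the check's cross-reference to mean the BMI > 30 clause. The dose section ties decreased compliance to the 40 tier, so the documents do not establish it.

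**Conclusion.** The inconsistency is real and lies in the current text. The daily check is 5 cmH₂O above the prescribed sigh pressure in each tier, no tolerance is stated, and part a repeats the higher pair with a conflicting BMI cut-off. Followed literally, the check cannot detect a default patient receiving the high-tier 40, and it allows 45 in the high tier, beyond what the comparison with earlier studies supports.

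This assumes that the patients named in the check are those in the 40 tier, and that therapists apply the limit as printed. Whether 40/45 is text left from another dose or an intended ceiling cannot be determined. No harm and no effect on the primary analysis is shown. The point should be corrected because the figure is a bedside safety threshold and the correction is cheap.

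**What to change.** In part b (VILI), set the daily check to a sigh plateau pressure no higher than 35 cmH₂O, or 40 for BMI > 35, moderate or severe abdominal distension, or prone position, with a small measurement tolerance stated as a number. Assign the tier at each check from the distension and prone status already collected daily. In part a, change the 40 (45, BMI > 30) clause to the same values and cut-off.

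If 40/45 is meant as a ceiling, say so under Intervention to be tested with the BMI > 35 cut-off, align the clause in part a, and extend the part a comparison and the part b overdistension text to cover 45.

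The cost is two text edits and somewhat more frequent adjustments, which the stated tolerance would limit. Specifying the sigh plateau pressure in daily item 3b would help document adherence, but it is optional.

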Each patient will be seen daily by research personnel from the time each patient is enrolled until day 28 or until the patient is discharged from the ICU, either to another floor in the hospital or home or dies. If a patient is transferred to a progressive care or step-down unit and continues to receive ventilation, the patient will be followed on a daily basis until the patient is extubated or dies or until day 28.

These daily visits will seek evidence of adverse events or complications per the study manual of procedure. If adverse events or complications have occurred they will be recorded on the adverse event case report form. Whether a patient experiencing an adverse event continues on the study or is withdrawn will be decided by the treating physician.

If the patient is discharged from the ICU before day 28 and is no longer receiving mechanical ventilation, research personnel will review medical records and/or contact

IRB Protocol: _____

Site PI: _____

Version Date: 2/9/2020

Page 26 of 34

the patient on day 28 to determine whether the patient has experienced any adverse events between the day the patient was discharged from the ICU and day 28.

The investigator will report all adverse events to the DCC within 24 hours of their occurrence. The local Institutional Review Board (IRB) will also be informed in a timely manner. The investigator will then submit a detailed, written report to the DCC and to the IRB no later than five days after the investigator discovers the event.

The DCC will report all serious, unexpected and study-related adverse events to the DSMB by fax or telephone within seven calendar days. A written report will be sent to the DSMB within 15 calendar days and these reports will be sent to investigators for submission to their respective IRBs. The DSMB will also review all adverse events during each scheduled interim analysis. The DCC will distribute the written summary of the DSMB's periodic review of adverse events to investigators for submission to their respective IRBs.

All patients in this study will be hospitalized in an intensive care unit. Accordingly, emergency care will be readily available at all times. The cost of treatment for all study-related adverse events will be covered by each individual hospital.

Potential benefits

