The rationale for this proposal comes from an extensive basic science and clinical literature supporting a new pathway by which ARDS developed as depicted in Figure 1. If this paradigm were correct most instances of ARDS are actually VILI that occurs because constant V_T ventilation alters surfactant which, in turn, causes atelectasis and provide the setting in which atelectrauma occurs. Adding sigh breaths will augment surfactant secretion into the alveolar space and could interrupt this pathophysiological process. If this study finds that sigh ventilation reduces ventilator-free days it will reduce the morbidity and possibly the mortality of victims of trauma who are at increased risk of developing ARDS.

IRB Protocol: _____

Site PI: _____

Version Date: 2/9/2020

Page 8 of 34

Hypothesis and Specific Aim:

Hypothesis:

Adding sigh breaths to usual invasive mechanical ventilation of victims of trauma who are at risk of developing ARDS will decrease the number of days they require invasive mechanical ventilation.

Specific aim:

To determine if including sigh breaths in the usual care of victims of trauma who are at increased risk of developing ARDS will increase ventilator-free days.

Methods

Study Design:

Prospective, randomized, concurrently controlled clinical trial.

Inclusion criteria:

Patients in an intensive care unit (ICU) as a result of injuries from penetrating or non-penetrating trauma who are intubated and receiving invasive mechanical ventilation who also have one or more of the following:

1. Traumatic brain injury
2. > 1 long bone (femur, tibia, humerus) fractures
3. Shock on arrival in the Emergency Department (systolic BP < 90 mmHg)
4. Lung contusion (as diagnosed in the admission history and physical exam)
5. Receipt of > 6 units of any blood product in the first 24 hours

Exclusion criteria:

1. Inability to obtain consent from the patient or his/her legally authorized representative (LAR)
2. Unwillingness of the treating physician to use sigh ventilation as all treating physicians must have equipoise with respect to the intervention
3. Under 18 years of age
4. Undergoing invasive mechanical ventilation for > 24 hours, excluding any time during which the patient was being ventilated in the operating room, MRI, CT or IR, as this could represent too long a delay in instituting the intervention for it to have a chance of being effective

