We initially estimated a need to enroll 916 patients in SiVent. This was based on the assumption that the number of ventilator-free days (VFDs) in the control arm of the study would be 11.75 days, with a standard deviation (SD) of 10.5 days. These assumptions were taken from a study by Wiedemann et al, (N Engl J Med, 2006) that also used VFDs as a primary endpoint in a study of ARDS patients.

The actual number of VFDs and SD for patients enrolled in the control arm calculated by the DCC at the time of the first interim analysis were 15 days and 9.9 days, respectively. Using these actual numbers, a power of 80%, and an observed withdrawal rate of 1% (which we did not account for in the initial sample size estimate but was observed in the first 300 patients enrolled), we determined that we would be able to meet acceptable statistical goals by enrolling 544 patients.

Data Analysis

The primary endpoint for the SiVent study is VFDs in the first 28 days following randomization, with the convention that mortality prior to day 28, regardless of when it occurs, is equated to 0 ventilator-free days. This composite outcome, abbreviated as VFD28 in the following, has been used in previous studies of ARDS and is recommended by data analysts in the ARDS Network [Schoenfeld D, Bernard G (2002), Statistical evaluation of ventilator-free days as an efficacy measure in clinical trials of treatments for acute respiratory distress syndrome. Crit Care Med 30: 1772-1777.]

Because the statistical distribution of VFD28 is usually not close to normal, the primary analysis of the difference between the 'Sigh' group and the control group can be based on the Wilcoxon rank-sum statistic. Additional analyses, taking into account

IRB Protocol: _____

Site PI: _____

Version Date: 2/9/2020

Page 18 of 34

covariates such as age, gender, smoking history, and characteristics of the trauma which resulted in the patient being put on mechanical ventilation, in addition to treatment group, will be carried out using least-squares regression. Non-normality of the outcome is unlikely to influence the results of such analyses because the sample size is expected to be in the 300-1000 range (for interim and final analyses).

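### The adverse-event withdrawal rule does not separate stopping the assigned ventilation from leaving the study, so harmed sigh-arm patients can drop out of the VFD28 comparison

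*Combined protocol and SAP*

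**What the plan says.** Under Risk management and emergency response, b. Surveillance and reporting, the combined protocol and SAP states: "Whether a patient experiencing an adverse event continues on the study or is withdrawn will be decided by the treating physician". What the patient may be withdrawn from is the study, not just the sigh breaths. Part a of the same section separately lets the research monitor take individual subjects out of the study.

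The document never uses the words blinded or open-label, but the treating physician can hardly be unaware of the arm. Exclusion criterion 2 reads "Unwillingness of the treating physician to use sigh ventilation as all treating physicians must have equipoise with respect to the intervention". On patients who leave the ICU for a procedure, Intervention to be tested says "Sigh breaths should be restarted on their return". The section on VILI risk has the sigh plateau pressure rechecked whenever the treating physician is concerned.

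The Sample size estimate uses "an observed withdrawal rate of 1% (which we did not account for in the initial sample size estimate" as an input to the revised total of 544. Data Analysis names the Wilcoxon rank-sum test for VFD28 but defines no analysis set. Endpoints assigns 0 for death before day 28 or assisted ventilation at day 28, and gives no value for a withdrawn patient. The VILI section relies on the interim monitoring of VFDs as a safeguard and notes that "the stopping rules for harm are less stringent than those for documenting benefit".

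**The concern.** The decision comes after randomization, is triggered by an adverse event, and is made by someone who knows the assignment. Only the sigh arm has an added study intervention to which an event can be attributed, so there is a reason to expect more such withdrawals in that arm. Patients with a pneumothorax, hypotension or worsening lung function are also those most likely to end with few or no ventilator-free days.

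If they leave without an outcome, the remaining sigh patients look better than the group that was randomized. A false finding of benefit becomes more likely and a true harm harder to detect. The loss is selective, so enrolling more patients to make up the number does not remove the bias.

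**Working it through.** **Inputs from the documents.** Sample size estimate: N = 544, power 80%, withdrawal 1%, control VFD28 mean and SD that "at the time of the first interim analysis were 15 days and 9.9 days, respectively". Interim Analyses: information times 0.33, 0.66 and 1.00; upper bounds 2.61, 2.65 and 2.66; lower bound −2.09 at each look.

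**Assumptions.** Allocation is 1:1 (no ratio is stated), so 272 per arm. A z-test on means stands in for the Wilcoxon test. The target difference is back-solved, because none is stated. Lost patients are spread evenly over the looks.

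**Step 1: the plan's own figure.** Without a target difference, 544 cannot be reproduced directly.
- Evaluable per arm: 544 × 0.99 / 2 = 269.28.
- SE = 9.9 × √(2/269.28) = 0.853 day.
- Implied difference at two-sided 5% and 80% power: (1.960 + 0.842) × 0.853 = 2.39 days.
- Forward check: for 2.4 days a two-sample t-test needs 538 patients, and 538/0.99 = 543.4, rounded up to 544.

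So 544 is consistent with treating withdrawals as lost outcomes. It does not prove it: a difference of 2.38 days gives 544 by the normal formula with no allowance at all.

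**Step 2: number withdrawn.** 0.01 × 300 = 3 in the first 300 patients; 0.01 × 544 = 5.44, or about 5, in the full trial.

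**Step 3: shift in the sigh mean.** Remove k patients who would have scored 0 from an arm of 272 with mean m. The mean rises by m·k/(272 − k).
- No true effect, m = 15: k = 5 gives 75/267 = 0.28 day (0.28/0.853 = 0.33 SE); k = 3 gives 45/269 = 0.17 day (0.20 SE).
- True loss of 2.39 days, m = 15 − 2.39 = 12.61: k = 5 gives 63.05/267 = 0.24 day; k = 3 gives 37.83/269 = 0.14 day.

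**Step 4: boundary crossing.** Group-sequential simulation, 2 million runs, with the plan's bounds:

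| Sigh patients lost (all true zeros) | Shift, no true effect | Crosses upper bound, no true effect | Crosses lower bound, true loss of 2.39 days |
|---|---|---|---|
| 0 | 0 | 1.0% | 80% |
| 2 | 0.11 day | 1.3% | 77% |
| 3 | 0.17 day | 1.5% | 75% |
| 5 | 0.28 day | 2.0% | 71% |

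**Step 5: check with the Wilcoxon test.** Single final look, no true effect, 20,000 runs, an assumed VFD28 distribution with mean 15, SD 9.9 and 22% zeros. Deleting the 5 lowest sigh values raises the chance of exceeding 2.66 from 0.4% to 0.9% and lowers the chance of falling below −2.09 from 1.9% to 0.8%. Deleting 14 (5% of the arm) takes the first figure to 3.9%. The direction agrees with Step 4, and the effect grows quickly if withdrawal rises.

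**The case against.** A reader might infer that the plan drops withdrawn patients from the primary test. No sentence says so. The 1% allowance suggests that they supply no outcome, but this remains an inference. Patient Follow-up Process sets follow-up for enrolled patients without listing an exception for withdrawal, day-28 status can be taken from records, and death before day 28 scores 0 whenever it occurs. None of this expressly covers a patient who has been withdrawn, so the gap stands, but as silence and not as a stated exclusion.

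A reader might also take the observed 1% as evidence that harmed sigh patients are already being lost. The document gives neither arm nor reason for it. Informed consent process describes another route: a representative who does not reaffirm telephone consent, or a patient who declines after regaining capacity. That route could account for some or all of the 1%. Control patients can be withdrawn too.

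Oversight also counts. The DSMB receives withdrawal rates, losses to follow-up, deaths and adverse events, and may recommend stopping without a boundary being crossed. A lopsided pattern could be noticed. That tempers the safety concern, but it does not restore missing outcomes to the final analysis.

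Finally, the five-patient case stacks every extreme, and even then the false-benefit rate of 2.0% is below a conventional one-sided 2.5%.

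**Conclusion.** The concern holds as a weakness in the rule: as written, it permits selective loss after randomization by a decision-maker who in practice knows the arm, and nothing in the analysis plan closes the gap. It should be corrected.

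The size is modest at the observed withdrawal rate. The five-patient figures are an upper bound, and the three-patient case still places every loss among sigh patients with a true score of 0. Both rest on 272 per arm, a z-test on means and the back-solved 2.39 days. The likely effect is smaller, although nothing in the plan keeps withdrawal at 1%. The documents do not support saying that the comparison is already biased or that withdrawn patients are in fact excluded.

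**What to change.** Leave clinical decisions about the assigned ventilation as they are. Reword Surveillance and reporting, and align Research Monitor with it, so that stopping the assigned ventilation, or removal from it by the physician or the research monitor, does not end outcome collection. Follow such patients to day 28 through the record review or contact already described in Patient Follow-up Process, and score them for VFD28, ICU-free days and mortality in their randomized group. Let only withdrawal of consent for data collection end follow-up, keeping data up to that point as permitted.

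In Data Analysis, state that all randomized patients are analyzed as randomized, and say how VFD28 is handled where consent withdrawal leaves it unknown. Report withdrawals by arm and reason, including those already observed.

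The cost is protocol wording and a little extra record review.
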